3.4.5 Follow-Up Period

Assessments to be performed during the follow-up period are detailed in the Schedule of Assessments (Table 7a and Table 7b). The follow-up period will last 3 years from the HSCT date for both patients who received and those who did not receive emapalumab, as detailed below.

Follow-up period: emapalumab treated patients

All emapalumab treated patients will enter the follow-up period:

- (i) Upon completion of treatment or engraftment, whichever comes first
- (ii) In case of premature treatment discontinuation for any reason

The follow-up period for patients who received emapalumab will consist of 6 visits: at 1 week \pm 2 days, 2 weeks \pm 2 days, 4 weeks \pm 2 days, 8 weeks \pm 1 week, 12 weeks \pm 1 week and 24 weeks \pm 2 weeks after last study drug administration (EoS visit) and 3 phone calls for survival observation at 1, 2 and 3 years after HSCT.

During the survival calls defined concomitant medications/procedures (i.e. any HSCT, blood product transfusion, stem cell boost, DLI or hematopoietic agents) and occurrence of GvHD since previous visit/call should be recorded.

The first follow-up visit will be 1 week \pm 2 days after last study drug administration or 1 week after EoT (in case of treatment discontinuation or engraftment before the last dosing day).

Follow-up period: non-emapalumab treated patients

In case treatment with emapalumab has not been initiated, patients will undergo an EoS visit (within 1 week from the last day in the monitoring periods) and enter the phone calls follow-up.

A patient can enter follow-up in the following occasions:

- (i) At the end of the monitoring (Day 42) or extended monitoring (Day 98).
- (ii) If they require a second HSCT anytime during the monitoring periods.
- (iii) If any prohibited medication is taken during the monitoring periods.
- (iv) In case of re-occurrence of malignant disease, GvHD diagnosis, uncontrolled infection or clinical manifestations of infections representing exclusion criteria at time of eligibility to treatment.

The follow-up period for non-emapalumab treated patients will consist of 4 phone calls at 6 months, 1, 2 and 3 years after HSCT. During the survival calls defined concomitant medications/procedures (i.e. any HSCT, blood product transfusion, stem cell boost, DLI or hematopoietic agents) and occurrence of GvHD since previous visit/call should be recorded.

End of Study Visit

Assessments to be performed during the EoS visit are detailed in the Schedule of Assessments (Table 7a and Table 7b).

- For emapalumab treated patients, the EoS visit correspond to the last follow-up visit (Follow-up visit 6) at week 24 \pm 2 days from last study drug administration.
- Non-emapalumab treated patients will require to attend the EoS visit within 1 week from the last day in the monitoring periods.

Table 2 Transition between periods in case of ANC < 500 cells/ μ L during the monitoring period

Monitoring	Treatment	Follow-up For emapalumab treated patients	Follow-up For non-emapalumab treated patients
CXCL9 above threshold + ANC <500 cells/ μ L 	Enter treatment period		Perform EoS visit and enter phone-calls follow-up period:
CXCL9 below threshold + ANC <500 cells/ μ L  Continue monitoring ✓ Unless a second HSCT is required ✓ As soon as ANC \geq 500, transition to extended monitoring Table 3		Enter follow-up period: ✓ Upon completion of treatment or engraftment during treatment, whichever comes first ✓ Upon premature treatment discontinuation for any reason	
 ✓ At the end of monitoring or ext monitoring period ✓ In case of re-occurrence of malignant disease, GvHD diagnosis, uncontrolled infection or clinical manifestations of infections representing exclusion criteria at time of treatment ✓ If a second HSCT is required ✓ If any prohibited med is taken during the monitoring periods

Table 3 Transition between periods in case of ANC \geq 500 cells/ μ L during the monitoring period

Monitoring	Extended Monitoring	Treatment	Follow-up For emapalumab treated patients	Follow-up For non-emapalumab treated patients
As soon as ANC \geq 500 cells/ μ L during monitoring, enter extended monitoring	CXCL9 above threshold + Signs of sGF 	Enter treatment period	Enter follow-up period: ✓ Upon completion of treatment or engraftment during treatment, whichever comes first	Perform EoS visit and enter phone-calls follow-up period: ✓ At the end of monitoring or ext monitoring period ✓ In case of re-occurrence of malignant disease, GvHD diagnosis, uncontrolled infection or clinical manifestations of infections representing exclusion criteria at time of treatment
	If CXCL9 below threshold Continue extended monitoring unless a second HSCT is required		✓ Upon premature treatment discontinuation for any reason	
 ✓ If a second HSCT is required ✓ If any prohibited med is taken during the monitoring periods

3.4.6 Unscheduled visit

Assessments to be performed during the unscheduled visit are detailed in the Schedule of Assessments (Table 7a and Table 7b). Unscheduled visits may be performed at any time during the study. Depending on the reason for the unscheduled visit, appropriate assessments will be performed based on medical judgment. After an unscheduled visit, the regular scheduled study visits must continue according to the planned visit and assessment schedule.

3.4.7 Withdrawal visit

Assessments to be performed during the withdrawal visit are detailed in the Schedule of Assessments (Table 7a and Table 7b). In case of premature withdrawal from the study for any reason (except informed consent withdrawal), patients should undergo a withdrawal visit within 1 week from the date of withdrawal.

3.5 Study duration and study end

The study will start with the act of signing the informed consent form and ends with the last phone call or last patient visit. The study is expected to last approximately 3 years from screening to the last phone call for each patient.

Study end is defined as the last patient last call at the end of the follow-up period (3 years) or at any time before the end of the follow-up period when the last patient completes their last visit.

3.6 Study committees

3.6.1 Independent Data Monitoring Committee

An IDMC has responsibility for safeguarding the interests of subjects by monitoring relevant data obtained in the study and making appropriate recommendations based on the reported data.

The IDMC will be fully operational prior to enrolment of the first subject into the study. The IDMC is composed of relevant experts (external to Sobi AG) and will review the data with the aim to assess the benefit/risk ratio of emapalumab administration and ensure patient safety.

The composition, frequency of meetings and operation of the IDMC is described in the IDMC charter.

3.6.2 Dose Decision Committee

A Dose Decision Committee (DDC) will be responsible for deciding the dose regimen to apply in cohorts 2 and 3 based on a review of PK, PD, efficacy and safety data. The DDC will confirm the appropriate dose and the addition of patients to the last cohort. The DDC is composed of relevant Sobi employees and external experts as necessary.

The composition, frequency of meetings and operation of the DDC is described in the DDC charter.

4 STUDY POPULATION

Children and adults, with malignant and non-malignant underlying diseases, receiving allo-HSCT, who are at high risk of GF, will be included in the study. Children less than 1 year old will be included in the study once the appropriate dose regimen has been determined in cohort 1, 2 or 3 and safety has been assessed by the IDMC. Patients will be included in the study if they meet all the inclusion criteria and none of the exclusion criteria below.

4.1 Inclusion criteria

1. Informed consent form signed by the patient (as required by law) or by the patient's legally authorized representative(s) with the assent of patients who are legally capable of providing it, as applicable.
2. Recipients of allogeneic HSCT and at high risk of GF, based on at least one of the following criteria:
 - Receiving reduced intensity conditioning (RIC) or non-myeloablative (NMA) conditioning, combined with a non-malignant disease or with a graft from Bone Marrow (BM).
 - *Ex vivo* T cell depleted graft.
 - Graft from mismatched unrelated or haploidentical donor.
 - Graft from Umbilical Cord Blood (UCB).
3. Patients requiring allo-HSCT with the following underlying diseases:
 - Malignant disease with high risk of GF, i.e. Acute Myeloid Leukemia (AML) and Acute Lymphoblastic Leukemia (ALL), with primary induction failure, second partial remission or relapse; Chronic Myeloid Leukemia (CML) in blastic phase (circulating blast or blast above 5% in biopsy); Non Hodgkin and Hodgkin Lymphoma and multiple myeloma with primary induction failure, second partial remission or relapse; myelodysplastic syndromes (MDS) and myeloproliferative disorders (MPD) with splenomegaly; myelofibrosis with portal hypertension pre-transplant; MDS/MPD overlap syndromes.
 - Non-malignant hematological diseases (e.g. autoimmune and metabolic disorders, aplastic anemia, Sickle cell anemia, Fanconi anemia, Diamond-Blackfan anemia, thalassemia, osteopetrosis, Wiskott-Aldrich syndrome, severe combined immunodeficiency, Hemophagocytic lymphohistiocytosis and other immunoregulatory disorders).
4. Male and female patients.
5. Children aged at least 1 year and adults. Once the appropriate dose has been determined in one of the three cohorts and safety has been assessed by the IDMC, children less than 1 year old may be included in the study.
6. Females of child-bearing potential, defined as all women physiologically capable of becoming pregnant, require the use of highly effective contraceptive measures from screening until 6 months after the last study drug administration.

4.2 Exclusion criteria

1. Pregnant (or planning to become pregnant) or lactating, female patients.
2. Body weight < 3 kg.
3. Underlying malignant disease with Karnofsky/Lansky performance status equal or less than 40 or an ECOG performance status equal or less than 3.
4. Patients presenting CXCL9 levels 10 times above the upper limit of the 95% CI of the normal range (reported in the CXCL9 assay laboratory manual) within 24 hours prior to HSCT.
5. Clinically manifested infections caused by typical and atypical Mycobacteria, Salmonella, Histoplasma capsulatum and Herpes Zoster on the day of HSCT.
6. Active or clinical suspicion of latent tuberculosis.
7. Concomitant diseases that, in the opinion of the Investigator, may interfere with the assessment of emapalumab safety or efficacy.

8. Receipt of a Bacille Calmette-Guerin (BCG) vaccine within 3 months prior to HSCT.
9. Receipt of a live or attenuated live (other than BCG) vaccine within 6 weeks prior to HSCT.
10. Current or scheduled administration of therapies known to potentially trigger a cytokine release syndrome within 21 days from HSCT.
11. Patients having received IFN γ during the last 2 weeks prior to HSCT and/or who require treatment with IFN γ .
12. Patients having received emapalumab during the last 6 months prior to HSCT, unless it is known that emapalumab is no longer detectable.
13. Patients having received kinase inhibitors (Janus kinase inhibitors [JAKi] or bruton tyrosine kinase inhibitors [BTKi]) one week (or 5 half-lives whichever is greater) prior to HSCT.
14. Intolerance to antimicrobial and viral infection prophylaxis.
15. Hypersensitivity to emapalumab or any of the excipients.
16. Ongoing participation in an interventional trial or administration of any investigational drug (within 3 half-lives of the investigational drug) with the exception of interventional trials involving supportive care such as probiotics or antiemetics, graft manipulation, or use of new combinations or new dosing of conventional therapies for conditioning and prophylaxis pre-HSCT.

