EXCLUSION CRITERIA	
 1. Pregnant (or planning to become pregnant) or lactating female patients. 2. Body weight < 3 kg. 3. Underlying malignant disease with Karnofsky/Lansky performance status equal or less than 40 or an Eastern Cooperative Oncology Group (ECOG) performance status equal or less than 3. 4. Patients presenting CXCL9 levels 10 times above the upper limit of the 95% interval (CI) of the normal range (reported in the CXCL9 assay laboratory manual) within 24 hours prior to HSCT. 5. Clinically manifested infections caused by typical and atypical Mycobacteria, Salmonella, Histoplasma capsulatum and Herpes Zoster on the day of HSCT. 6. Active or clinical suspicion of latent tuberculosis. 7. Concomitant diseases that in the opinion of the Investigator may interfere with the assessment of emapalumab safety or efficacy. 8. Receipt of a Bacille Calmette-Guerin (BCG) vaccine within 3 months prior to HSCT. 9. Receipt of a live or attenuated live (other than BCG) vaccine within 6 weeks prior to HSCT. 10. Current or scheduled administration of therapies known to potentially trigger a cytokine release syndrome within 21 days from HSCT. 11. Patients having received IFNγ during the last 2 weeks prior to HSCT and/or who require treatment with IFNγ. 12. Patients having received emapalumab during the last 6 months prior to HSCT, unless it is known that emapalumab is no longer detectable.

	
13. Patients having received kinase inhibitors (Janus kinase inhibitors [JAKi] or bruton tyrosine kinase inhibitors [BTKi]) one week (or 5 half-lives whichever is greater) prior to HSCT.
 
14. Intolerance to antimicrobial and virus infection prophylaxis.
 
15. Hypersensitivity to emapalumab or any of the excipients.
 
16. Ongoing participation in an interventional trial or administration of any investigational drug (within 3 half-lives of the investigational drug) with the exception of interventional trials involving supportive care such as probiotics or antiemetics, graft manipulation, or use of new combinations or new dosing of conventional therapies for conditioning and prophylaxis pre-HSCT.

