3 OVERALL STUDY DESIGN AND PLAN

3.1 Overall study design

This study is an open-label, single arm, sequential dose cohorts, proof of concept phase 2 study and it enrolls children and adults receiving allogeneic HSCT who are at high risk of graft failure. Children less than 1 year old will be included only after the appropriate dose regimen has been determined in one of the three cohorts and safety assessed by an Independent Data Monitoring Committee (IDMC).

The study is comprised of the following study periods: screening (Day -21 to Day -8), allogeneic HSCT Day 0, monitoring period for primary GF (Day 1 up to Day 42), extended monitoring for secondary GF (up to Day 98), treatment period (up to 56 days) and follow-up period of 3 years after HSCT. The overall study design is shown in Table 1.

Patients presenting CXCL9 levels above a defined threshold and an ANC below 500 cells/ μ L will be eligible to receive emapalumab during the monitoring period (Day 1 to Day 42).

Patients presenting CXCL9 levels above thresholds and signs of secondary GF (i.e. donor chimerism drop of at least 10% for 2 consecutive measurements and/or absolute neutrophil count [ANC] below 500 cells/ μ L and/or thrombocytopenia below 30000/ μ L not explained by any other reason than potential graft rejection) during the extended monitoring period (up to Day 98) will also be eligible to receive emapalumab. Pre-emptive treatment for secondary GF is optional.

A maximum of 3 cohorts is foreseen to determine the appropriate dose to pre-emptively treat primary GF. Data will be analyzed after the last patient completes emapalumab treatment in each cohort. After each cohort, the Sponsor will decide whether to stop the study or to add an additional cohort with dosing regimen adaptation based on observed PK/PD profile and benefit risk profile.

Once the appropriate dose has been determined a maximum of 6 evaluable additional patients may be added to the corresponding cohort to explore the potential benefit of emapalumab in preventing primary GF.

Patients will be stratified at screening in order to include at least 40% malignant and 40% non-malignant (by means of an interactive response technology).

Table 1: Overall study design for cohort 1, 2 or 3

SCREENING	HSCT	MONITORING (Primary GF)	EXTENDED MONITORING (Secondary GF)	FOLLOW-UP (for emapalumab treated ² and non-emapalumab treated patients ³)
Day -21 to Day-8	Day 0	Day 1 to Day 42	Up to Day 98 ¹	3 years from HSCT

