3.4 Study periods

3.4.1 Screening Period

Screening starts with the signature of the informed consent by the patient or by the patient's legally authorized representative prior to any study-related procedures. It is the responsibility of the investigator/delegate to obtain written informed consent from each subject or legally authorized representative(s) after adequate face-to-face explanation of the objectives, methods, and potential hazards of the study.

It is permitted to re-screen patients once if the reason for non-eligibility was transient (e.g. abnormal laboratory test, insufficient wash-out period of a forbidden medication). All screening assessments must be repeated at the time of re-screening, except chest X-ray which should be repeated if older than 21 days. For patients below 30 kg, procedures performed during the screening period may be used to satisfy screening requirements if re-screening is performed within 21 days from the latest results.

Chest X-rays performed as part of medical practise prior to screening may be used to satisfy screening requirements if they are performed within the screening window of 21 days before HSCT.

Patients who have given written informed consent will undergo screening assessments between Day -21 and Day -8 prior to HSCT and will be assessed for eligibility to enter the study. Eligibility is also assessed prior to HSCT (Day 0). Patients will be stratified in order to include at least 40% of the patients with malignant and 40% with non-malignant disease (by means of an interactive response technology). Stratification will allow to explore the appropriate dose inhibiting IFN γ production in a similar number of patients presenting with malignant or non-malignant disease in each cohort. Assessments to be performed during screening are presented in the schedule of assessment (Table 5a and Table 5b).

A patient screening log will be maintained by the investigator for all eligible and non-eligible patients, with specification of reasons for non-eligibility, if applicable.

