3.4.2 Allogeneic HSCT

Assessments to be performed on the day of HSCT are presented in the schedule of assessment (Table 5a and Table 5b) Patient's eligibility is assessed by checking inclusion/exclusion criteria prior to HSCT on Day 0. A patient is considered included in the study if he/she meets all inclusion/exclusion criteria prior to HSCT.

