12.3 Patients stratification

Patients will be stratified into two groups at screening (at least 40% malignant and 40% non-malignant) by means of an interactive response technology. Stratification will allow to explore the appropriate dose inhibiting IFN γ production in a similar number of patients presenting with malignant or non-malignant disease in each cohort.

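### Exclusion criterion 3 points the ECOG inequality the wrong way: as written it bars malignant patients scored ECOG 0 to 3, in a plan that needs at least 40% malignant patients

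*Combined protocol and SAP*

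**What the plan says.** Section 4.2, criterion 3, excludes "Underlying malignant disease with Karnofsky/Lansky performance status equal or less than 40 or an ECOG performance status equal or less than 3". The synopsis has the same rule, ending in "Eastern Cooperative Oncology Group (ECOG) performance status equal or less than 3".

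The rule is binding. Section 4 states: "Patients will be included in the study if they meet all the inclusion criteria and none of the exclusion criteria below". Section 3.4.2 adds: "A patient is considered included in the study if he/she meets all inclusion/exclusion criteria prior to HSCT". Tables 5a and 5b schedule the review of the criteria at screening and on Day 0.

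The plan also sets out to recruit malignant disease. Inclusion criterion 3 in section 4.1 opens with "Malignant disease with high risk of GF, i.e. Acute Myeloid Leukemia (AML) and Acute Lymphoblastic Leukemia (ALL), with primary induction failure" and goes on to other malignancies. Section 12.3 sets the quota: "Patients will be stratified into two groups at screening (at least 40% malignant and 40% non-malignant) by means of an interactive response technology". Sections 3.1 and 3.4.1 repeat it. Section 8.1 lists ECOG, with no age limit, as a baseline characteristic for malignant disease; Karnofsky and Lansky are not on that list.

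**The concern.** The criterion uses one direction of inequality for two scales that run in opposite directions. The Karnofsky/Lansky limb removes the patients with the poorest function. The ECOG limb, as worded, removes those with the best function and keeps the worst. The limbs are joined by *or*, so a Karnofsky/Lansky score above 40 does not rescue a patient who also has an ECOG score of 0 to 3.

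Nothing in the documents repairs this. The wording is the same in both places, so it is not a slip in one copy. The section 4.2 entry in the summary of changes covers criteria 10 and 16 only. The list of pre-enrolment measures in section 10.2.5.1 does not mention performance status.

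A site that applies the text literally has almost no malignant patients to offer. A site that reads through to the intent enrols patients whom the protocol excludes on paper, and must decide for itself how to treat grade 3.

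**Working it through.** **Assumption.** ECOG runs from 0 (best) to 4 (worst) in living patients. The protocol does not define the scale. That grades 0 to 3 are barred follows from the inequality and a scale starting at 0. The conflict between the two limbs also needs the direction of the scale.

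**Step 1: what each reading does to the ECOG limb.** A and B are the two ways of restoring the direction.

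| ECOG grade | Literal text (3 or less excluded) | Reading A (3 and above excluded) | Reading B (only above 3 excluded) |
|---|---|---|---|
| 0 | out | in | in |
| 1 | out | in | in |
| 2 | out | in | in |
| 3 | out | out | in |
| 4 | in | out | out |

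- The literal text bars 4 of 5 grades.
- It differs from A at grades 0, 1, 2 and 4 (4 of 5), and from B at all 5.
- A and B differ only at grade 3.
- Every grade admitted under A or B is barred by the literal text.

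**Step 2: the plan's own patient numbers (section 12.1).** Treating 4 patients per cohort at a trigger rate of 10 to 30% needs 4 / 0.10 = 40 and 4 / 0.30 = 13.3, rounded up to 14. The plan states 15 to 40, so its range is reproduced to within a patient or two. The stated maximum for the study is about 250. Criterion 3 changes none of these figures.

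**Step 3: literal deviations if sites read through.** Suppose every malignant patient has an ECOG score, as section 8.1 implies, and the 40% floor is met within the group counted. By step 1, every malignant patient included under A or B is then a literal deviation:

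- Cohort of 15: 0.40 × 15 = 6
- Cohort of 40: 0.40 × 40 = 16
- Study of 250: 0.40 × 250 = 100

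**Step 4: how many patients fall in the disputed grade.** The two 40% floors put the malignant share between 40% and 60%: 6 to 9 of 15, 16 to 24 of 40, and 100 to 150 of 250. The documents give no grade 3 share, so the last column is only an assumed range.

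| Group | Patients per 1% of malignant patients at grade 3 | At an assumed 1 to 10% |
|---|---|---|
| Cohort of 15 | 0.06 to 0.09 | 0.06 to 0.9 |
| Cohort of 40 | 0.16 to 0.24 | 0.16 to 2.4 |
| Study of 250 | 1.0 to 1.5 | 1 to 15 |

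**The case against.** The strongest reply is that this is a wording slip which any transplant physician would see through, and that it changes no result. Much of that is fair.

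- **Analysis.** Section 12.4 does not remove eligibility deviations from the All evaluable population, which is the primary set. The Per protocol population is affected only if such deviations are classed as major because they might influence the primary efficacy endpoint, and no such effect is claimed. The dose decision, the interim rules and the sample size are untouched.
- **Quota.** The conflict with the 40% floor is one of effect, not of logic. A malignant patient scored only on Karnofsky/Lansky, above 40, is not caught by the ECOG limb, so the floor is not strictly unreachable.
- **Boundary.** Both limbs say *equal or*. Reversing only the direction word leads to reading A, while B also requires dropping *equal*. A is therefore the more natural repair on the text.
- **Counts.** The 6, 16 and 100 are conditional. They need every malignant patient to be scored on ECOG and all sites to read through. The cohort figures also apply within each cohort a floor that is stated for the study; similar numbers per cohort appear only as the purpose of stratification. The 100 uses the maximum enrolment, so it is not an expected count. The grade 3 range only scales an assumed share.
- **Schedule.** The lack of a separate performance-status row in Tables 5a and 5b is not a gap in itself, because the eligibility review covers criterion 3.

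These points limit the consequences but do not remove the error. Even if A is the likelier repair, sites should not have to infer an eligibility boundary, and the sponsor still has to state it.

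**Conclusion.** The concern holds. A binding eligibility rule is wrong as written, in both places where it appears, for one of the two strata the plan must fill. The literal ECOG limb bars 4 of 5 grades and contradicts the Karnofsky/Lansky limb of the same sentence. In effect it also works against inclusion criterion 3 and the 40% malignant floor.

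The intended direction can be inferred from the other limb and the quota. The treatment of grade 3 cannot be settled with certainty from the text.

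The conclusion rests on the usual direction and range of the ECOG scale. The deviation counts rest in addition on section 8.1 being followed and on sites reading through. The correction is needed because the rule itself is wrong, not because of any demonstrated bias in the efficacy or dose results.

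**What to change.** Reword the ECOG limb so that it and the Karnofsky/Lansky limb exclude the same end of function, consistent with the malignant quota. State the boundary explicitly, including whether the boundary grade is excluded, and use the same words in the synopsis and section 4.2. The cut-off is for the sponsor to set.

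It would also help to add one sentence saying which scale applies to which patients, in line with section 8.1. That is useful detail rather than part of the error.

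The cost is one clause in two places, the optional sentence, a memo to sites and an updated eligibility check, with ethics approval under section 13.6 if the amendment counts as substantial. No extra patients, procedures or analyses are needed.
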